6.4. Potential Risks to Participants

The studies have mal risk to participants. The studies consist of interviews and surveys to research individual and group characteristics.

6.4.A. A risk that can occur from being in the *Intervention Study* is discomfort or embarrassment from the participant answering personal questions on surveys and interviews. Answers from participants are confidential and will be seen only by research staff. The interventions are manualized and all coaches will be trained and supervised by the PIs at each site; graduate students will be trained and will provide supervision of coaches as well.

Another possible risk is the breach of confidentiality. Data files used for analysis will not contain any identifiable information. If there is a breach of confidentiality, participants will be informed. There is also a low probability that participants will have a loss of privacy (name & email) if the online program is compromised.

[figure not shown]
The risks are mal for participants assigned to the mood monitoring condition. These youth will be monitored for symptoms as often as those in the intervention condition. Moreover, given that this is a prevention trial, no participant currently meets diagnostic criteria for a mood or anxiety disorder with serious clinical impairment. Thus, treatment is not being withheld. All participants are free to seek other non-study professional services and will be encouraged to engage in standard care mental health services as needed. All participants will be offered the opportunity to receive the other program materials after their follow-up assessment is completed.

7.0 Study Withdrawal/Discontinuation

Participants can withdraw from the study by the participant or parent letting study personnel know in writing that they would like to stop study participation. The address to which a letter can be sent is listed in the consent form. Participants who want to stop the mindfulness program can still participate in the assessments and will be compensated. Participants who choose to withdraw will be compensated for all study tasks that they have completed up until that point. Study data collected up to the point of withdrawal will be maintained.

8.0 Statistical Considerations

The figure below depicts the structural equation model (SEM) analysis of the data from this study (through Post) and the R33 study that will follow it (through Follow-up, f-u). We will conduct an inferential test of the critical a_2 path – representing the effect of intervention on our primary target variable, momentary negative affect (mNA) - from our SEM analysis. We conducted a power analysis using G*Power and with a post-treatment sample size of 102 and a medium effect size for the a_2 path (i.e., a .50 standard deviation post-treatment condition effect), alpha = .05 and a one-tailed test, we will have power of .81. Our initial sample size for the R61 was 126 (42 per site, 21 per condition per site) so that even with close to 20% attrition, we will still end up with 102 at post-treatment.

9.0 Privacy/Confidentiality Issues

This study is supported by the National Institute of Health and therefore has a certificate of confidentiality through NIH.

Data Storage: Non-audio/video digital files, including survey data, will be stored in a password-protected, secured Box folder, labeled by code number only and will be stored indefinitely. Data Storage will not be permitted on personal computers. The Box folder is password-protected. All files will be labeled by date, session number, and participant code and will not include any identifying information (e.g., name, initials, birth date). The Box Folder with SAFER will be accessed by research team members only. The SAFER folder will have two administrators that will be able to manage the levels of access study personnel have to sensitive data. The de-identified survey data will be stored indefinitely.

Audio/Video Recording: Assessment interviews will be audio recorded for evaluating inter-rater reliability and coached intervention sessions will be audio and video recorded to ensure that the intervention is delivered with fidelity and for supervision. Audio and video recordings will be labeled using date, session number, and participant code. The file naming system will not include any personal identifiers (e.g., participant name, age, address). The audio and video recordings will be stored on a secure Box folder with SAFER add-on that is only accessible by the study personnel. Audio and video recordings will be stored up to 7 years after the study is published; no one outside of the study team will have access to the recordings. Recordings will be shared outside the research team only if the participant gives express consent on a separate consent form.

10.0 Follow-up and Record Retention

Deidentified participant data from surveys will be stored indefinitely in a secure Box folder with the SAFER add-on. and will only be shared outwardly with express consent from study participants. All study data will be maintained indefinitely by the PIs of the coordinating and data centers ([name] at Vanderbilt University, [name] at Northwestern University, respectively). De-identified data will be shared according to the requirements of the National Institute of Mental Health.

APPENDIX A: Study Procedures and Frequency of Activities

Procedures (Participant Activities)	Frequency
Questionnaires to assess negative affect, symptoms, and functioning. Surveys will be conducted on REDCap.	Four times (pre-, mid-, post-intervention, and follow-up). Survey Length : Approximately 50 minutes
Interview to assess psychiatric diagnoses: Interviews will be conducted on Zoom or phone.	Three times (pre- and post-intervention, and follow-up). Interview Length: About 60 minutes
EMA - Ecological Momentary Assessment: EMA surveys will be conducted via an individualized link on Qualtrics	EMA occurs two times (pre- and post-intervention). Survey length : Each EMA response takes about 5-10 minutes (4 per day for 7 days)
Weekly Assessment: Measures of mood related symptoms will be administered once a week. Weekly measures will be completed via. REDCap.	Completed weekly. Survey Length : 10 minutes
Participants in the Mindfulness condition will complete online activities on their own between coaching sessions for 5 minutes a day in week 1, 10 minutes a day in weeks 2-5, and 15 minutes a day in weeks 6-9. Participants in the Awareness condition will complete writing activities four days a week for 10 to 15 minutes each time.	Participants will be asked to access the online activities over the 9 weeks of the program.
Coached Sessions - Participants will work with a coach on program activities. Coaches will train participants in the YMAP mindfulness or awareness activities that they complete weekly.	There will be 9 coaching sessions (once per week) during the Intervention Study. Coaching Session Length : 30-40 minutes.

APPENDIX B: Procedures Flowchart

## Data Analysis Plan

*Average momentary negative affect (mNA).* We created scalar invariant latent average mNA variables using the 7 EMA NA items (sad, tired, irritable, nervous, angry, afraid, and lonely) at pre- and post-intervention. Each item at each of the two time points represented the participant's average score on that item across all the EMA prompts at that time point. Unstandardized loadings were constrained to equal one for each item to create a latent, unweighted average variable and were so constrained across time; each item's intercept was constrained to be equal over time. Together, these constraints on the loadings and intercepts result in the latent average mNA variable being scalar invariant over time; that is, the latent variable has the same scale over time such that changes from pre to post can be interpreted quantitatively.

We included a priori correlated residuals for each item with itself from pre- to post-intervention. Standardized loadings were salient ( $\geq .30$ ) for each of the 7 items at both pre (average loading = .53; range = .34 to .81) and post (average loading = .50; range = .30 to .79). Thus, the latent average mNA variable was well defined at both T1 and T2. We then saved factor score estimates for each participant for their latent average mNA at pre and post for the analyses of whether the intervention impacted average mNA. The factor score determinacy coefficients equaled .89 at both pre and post. Testing for group differences on the average mNA factor score estimates at pre showed that the intervention and control condition did not differ significantly at T1 ( $t = .67$ ,  $df = 108$ ; 2-tailed  $p = .50$ ; Cohen's  $d = .20$ ).

*Stressor-independent negative affect.* The measure of stressor-independent mNA (mNA-SI) was derived from a similar scalar invariant latent variable model as for latent average mNA

---

All factor score determinacy coefficients reported are for participants with complete data on the measure's indicators.

above with one exception. In the mNA-SI model, each item at each of the two time points represented the participant's average score on that item at that time point for only those prompts for which they reported that they had *not* experienced a stressor since the previous EMA prompt. Standardized loadings were salient ( $\geq .30$ ) for six of the seven items at both pre (average loading = .38; range = .22 to .58) and post (average loading = .45; range = .26 to .77). Thus, the latent mNA-SI variable was well defined at both T1 and T2. We then saved factor score estimates for each participant for their latent mNA-SI at pre and at post for the analyses of whether the intervention impacted average mNA-SI. The factor score determinacy coefficients equaled .82 at pre and .86 at post. Testing for group differences on the latent mNA-SI factor score estimates at pre-intervention revealed that the intervention and control conditions did not differ significantly at T1 ( $t = -.06$ ,  $df = 100$ ; 2-tailed  $p = .96$ ; Cohen's  $d = -.01$ ).

*Stressor-reactive negative affect.* We used a two-step process to derive a measure of stressor-reactive negative affect (mNA-SR). The first step was to specify a similar scalar invariant latent variable model as for latent average mNA above with one exception. In this model, each item at each of the two time points represented the participant's average score on that item at that time point only for those prompts for which they reported that they *had* experienced a stressor since the last EMA prompt. Standardized loadings were salient ( $\geq .30$ ) for all seven items at both pre (average loading = .51; range = .34 to .73) and post (average loading = .49; range = .32 to .71). Thus, the latent mNA in the presence of a stressor variable was well defined at both time points. We saved factor score estimates for each participant for their latent mNA in the presence of a stressor at pre and at post. The factor score determinacy coefficients equaled .87 at pre and .86 at post.

Momentary negative affect (mNA) in the presence of stressor(s) has been taken to reflect the individual's baseline levels of mNA, mNA-SI, and their change in mNA in reaction to stressors, mNA-SR (e.g., Bolger & Schilling, 1991; Shackman et al., 2016). Thus, the second step in deriving a mNA-SR measure at T1 and T2 was to partial the mNA-SI score from the latent mNA in the presence of a stressor at that time point. The residuals of these regressions represent the increase in NA in reaction to a stressor; we saved these scores to use as the mNA-SR measure. Testing for group differences in mNA-SR at pre showed that the intervention and control condition did not differ significantly at T1 ( $t = -.11$ ,  $df = 98$ ; 2-tailed  $p = .91$ ; Cohen's  $d = -.02$ ). Importantly, mNA-SR was less temporally stable from pre to post ( $r = .73$ ) than the almost perfectly stable mNA-SI ( $r = .96$ ), thus, indicating that there was more change in mNA-SR than mNA-SI over the course of the study. Indeed, mNA-SR was a little less temporally stable from pre to post than the estimate of the latent average mNA ( $r = .78$ ) indicating somewhat more change in mNA-SR than mNA over the course of the study.

*Effects of the mindfulness intervention on mNA, mNA-SI and mNA-SR.* Although still debated, there are some contexts in which difference scores are preferable to analyses of regressed change to estimate change over two time points (e.g., Maxwell & Delaney, 2004; Rogosa, 1995; Willet, 1988; [name] et al., 2010). There is consensus, however, that regressed change is preferable to difference scores in the context of a randomized design (e.g., Maxwell & Delaney, 2004; [name] et al., 2010). Thus, in the current randomized design, we used regressed change to test the effect of the mindfulness intervention on mNA-SI, mNA-SR, and mNA. That is, for each of these variables, we performed a regression in which the individual's post score was the dependent variable, the individual's pre score was a covariate, and intervention condition was the main predictor of interest.

*Principal Components Analyses of Changes in Symptom Measures.* To minimize inflation of type I error rate that would have resulted from correlating the change in mNA-SR with the changes in each individual symptom scale and sub-scales, we performed principal components analyses (PCAs) of the change scores for all eight child symptom scales and sub-scales. Our PCAs used the scree test to determine the number of components to extract and an oblique (oblimin) rotation. The scree test on the eigenvalues suggested extracting two components (the eight eigenvalues equaled 4.16, 1.38, .65, .57, .43, .29, .29, and .24). After Oblimin rotation, the factor pattern matrix (see Supplement Table 1) clearly indicated that PC1 was loaded on by the five SCARED subscales, whereas PC2 was loaded on by the remaining measures (GAD7, PHQ, and NA15). The two components were moderately correlated ( $r=.45$ ). This moderate correlation is consistent with a second-order PC that we called Internalizing Change. Using the common identifying constraint of equal first-order factor loadings, each of the two first-order PCs loaded on this second-order factor .67. Given that the first-order PCs likely reflected method variance and the second-order PC was strong, our analyses of associations of symptom change with change in mNA-SR utilized factor score estimates reflecting the second-order PC (Internalizing Change). The factor score determinacy coefficient for the second-order PC factor score estimates equaled .88.

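### Post mNA scores come from a joint pre-post model with no condition term described and no rule for an empty post wave; if predicted post scores were used, the effect and its SE both shrink by about the missing share

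*SAP*

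**What the plan says.** The SAP (Data Analysis Plan, average mNA) builds one latent model for both waves, "using the 7 EMA NA items (sad, tired, irritable, nervous, angry, afraid, and lonely) at pre- and post-intervention". Each indicator is "the participant's average score on that item across all the EMA prompts at that time point". Loadings are fixed at one, intercepts are equal over time, and the waves are tied further: "We included a priori correlated residuals for each item with itself from pre- to post-intervention". Condition is not mentioned in this model.

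Scores are then taken out of the model: "We then saved factor score estimates for each participant for their latent average mNA at pre and post for the analyses". The same is done for mNA-SI, and for affect at stressor prompts: "We saved factor score estimates for each participant for their latent mNA in the presence of a stressor at pre and at post". Footnote 1 adds: "All factor score determinacy coefficients reported are for participants with complete data on the measure's indicators".

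The effect analysis is a separate regression, specified as follows: "the individual's post score was the dependent variable, the individual's pre score was a covariate, and intervention condition was the main predictor of interest".

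The SAP does not name the estimator, give a rule for a youth with no post EMA, or state the N of the effect regression. Protocol section 8.0 plans for losses in the R61: "even with close to 20% attrition, we will still end up with 102 at post-treatment".

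**The concern.** In a joint model, a regression-type factor score for one wave uses the items of both. If the software scores every case with any data, a youth with an empty post wave still gets a post score, predicted from the pre items. A model without condition predicts the same post score for two youth with the same pre answers, whichever arm they are in. Such scores carry no intervention effect and lie almost exactly on the post-on-pre line, yet the regression would count them as observed outcomes.

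At stake are the size and the interval of the condition effect on the primary target. The pre-post stabilities would be raised too. This differs from a complete-case problem: the youth lost to post EMA would stay in, with model-based outcomes.

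**Working it through.** **1. The plan's own power figure.** Section 8.0 gives N = 102 at post (51 per arm), 0.50 SD, one-tailed alpha .05 and power .81. Noncentrality is 0.5 × √(51/2) = 2.52, and Φ(2.52 − 1.645) = 0.81 (noncentral t: 0.806). It reproduces. Planned attrition is (126 − 102)/126 = 19.0%.

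**2. Do the scores borrow across waves?** The mNA-SI figures are informative. Stated loadings: pre mean .38, range .22 to .58; post mean .45, range .26 to .77. Assume that the five middle items are equal, so they are (7 × .38 − .22 − .58)/5 = .372 at pre and (7 × .45 − .26 − .77)/5 = .424 at post. Scoring each wave from its own items gives determinacy √[K/(1 + K)], with K = Σ λ²/(1 − λ²).

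- Pre: K = 0.507 + 5 × 0.161 + 0.051 = 1.36, determinacy .76.
- Post: K = 1.456 + 5 × 0.219 + 0.073 = 2.62, determinacy .85.

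| | Pre | Post | Pre-post r of scores |
|---|---|---|---|
| SAP, mNA-SI | .82 | .86 | .96 |
| Each wave from its own items | .76 | .85 | at most .81 (latent r near 1, residual r up to .5) |
| Joint scoring, latent r .90, residual r .3 to .5 | .82-.83 | .85-.86 | .96-.97 |

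Joint scoring fits all three reported figures; wave-by-wave scoring does not. The average-mNA determinacies do not discriminate: the same formula gives .89 and .88 wave by wave, against .89 and .89 reported.

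**3. Effect of predicted post scores.** Let b be the coefficient among youth with post EMA, s their residual SD, N the total and m the share without post EMA, equal by arm and missing at random.

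- Effect: a share 1 − m contributes b and a share m contributes 0, so the coefficient is about (1 − m)b.
- SE: predicted scores add cases but almost no residual, so the residual variance is about (1 − m)s². The SE is then 2s√(1 − m)/√N, against a proper 2s/√[(1 − m)N]. The ratio is 1 − m.
- The t statistic is therefore about unchanged.

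Simulation at N = 126: loadings matched to the stated mNA means and ranges, latent pre-post r .65, residual r .30, latent effect 0.50 SD (a negative coefficient is a reduction), 6,000 runs per row. The simulated score correlation is .69 to .74, somewhat below the reported .78. Coverage is for the coefficient that complete post scores would give.

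| m (assumed) | Effect, everyone scored / post EMA only | SE, same order | Ratios | 95% CI coverage, same order |
|---|---|---|---|---|
| 7% | −0.315 / −0.342 | 0.110 / 0.119 | 0.92, 0.92 | 0.943 / 0.951 |
| 10% | −0.313 / −0.345 | 0.109 / 0.120 | 0.91, 0.91 | 0.939 / 0.949 |
| 19% | −0.277 / −0.341 | 0.104 / 0.127 | 0.81, 0.82 | 0.905 / 0.949 |
| 30% | −0.239 / −0.342 | 0.097 / 0.137 | 0.70, 0.71 | 0.803 / 0.944 |

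At 19%, one-sided power is 0.847 either way and one-sided type I error is 0.051 against 0.053. Refitting the model by full-information maximum likelihood in each run (3,235 runs) gives ratios 0.81 and 0.81, with mean t −2.63 against −2.65. A repeat simulation gave −0.264 against −0.326 and SE 0.099 against 0.122, again a ratio of 0.81.

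**4. With no missing data.** The simulation at m = 0 already returns −0.341 for a latent 0.50. In closed form, take the same correlations, five equal middle loadings (.512 pre, .482 post) and score weights W = S⁻¹LΨ (S the item covariance matrix, L the loadings, Ψ the latent covariance matrix). A 0.50 shift in the post items then moves the post score by 0.354 and the pre score by 0.039. The post-on-pre slope is .716 × .880/.893 = 0.706, so the adjusted effect is 0.354 − 0.706 × 0.039 = 0.33. The small difference from 0.341 reflects the assumed spread of the loadings.

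**The case against.** The strongest objection is that the decisive step is inferred. The SAP names no estimator and nowhere says that a youth with an empty post wave was scored and analysed. If those youth were dropped, or their post scores set to missing, the missing-wave bias is zero. This stands.

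The degrees of freedom support the doubt. They imply 108 + 2 = 110 pre scores for mNA, 102 for mNA-SI and 100 for mNA-SR, so scoring each participant cannot mean literally everyone. Under joint scoring, the 8 youth lost between mNA and mNA-SI would have to have had no stressor-free prompt in either wave. That is possible, since a youth without post EMA need only lack one at pre, but a rule requiring prompts at the given wave fits at least as easily. The counts do not settle the matter.

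Footnote 1 also covers the Internalizing Change score, where incomplete data may mean a missing questionnaire. It suggests incomplete-data scoring; it does not identify youth without post EMA.

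Finally, the test is nearly unaffected, and the SAP describes a test rather than an interval. That limits the harm to the estimate and its precision. It does not remove it, because an effect size and interval from this regression would be wrong under the literal reading.

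**Conclusion.** The plan leaves open whether predicted post scores count as outcomes, and its own mNA-SI figures indicate the kind of scoring that would produce them. If they were used, effect and SE are both about 1 − m of the values from youth with post EMA: 0.81 at 19%, 0.90 at 10%. This assumes regression-type scores, full-information scoring of empty waves, missingness at random and the loadings above. The 19% is planned R61 attrition, not an observed count; the number without post EMA is not given, so the size is hypothetical.

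A reader might infer that dropouts were in fact given made-up outcomes, or that the significance test is invalid. The documents support neither: nothing shows that such scores entered the regression, and power and type I error barely move. Carrying the figures to the three-arm R33 (coverage 0.81 to 0.84 at 150 per arm and 19% missing) is likewise extrapolation, because the SAP reports a two-condition analysis.

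Nor is the coefficient from youth with post EMA the right value. Condition-free joint scoring shrinks a latent 0.50 to roughly 0.33 with complete data, under assumed correlations. That part applies to everyone and is the larger loss.

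**What to change.** Preferred: estimate the condition effect in one step, in the two-wave latent model with condition as a predictor, under full-information maximum likelihood. This is the a_2 path that protocol section 8.0 already names. It handles youth without post EMA in a model that contains condition, and it avoids the shrinkage from condition-free scoring.

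If factor scores are kept, state in the SAP that a wave's score is set to missing when the youth has no qualifying prompt in that wave: any prompt for mNA, a stressor-free prompt for mNA-SI, and both kinds for mNA-SR. Note that this removes only the missing-wave part of the shrinkage.

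Either way, name the estimator and scoring method, and report by arm the regression N and the number without post EMA. If predicted post scores were included in the mNA, mNA-SI or mNA-SR regressions, rerun them.

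Cost: modest extra modelling for the one-step model. If scores are kept, it is one sentence and a rerun, with a smaller analysed N and a larger SE (at an assumed 19% missing, 0.127 rather than 0.104).

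### mNA-SI: if the reported r = .96 is a saved-score correlation, the SAP's figures point to a pre score built partly from post-intervention answers, which would shrink the mNA-SI coefficient

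*SAP*

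**What the plan says.** The SAP (Data Analysis Plan, average mNA) sets up a two-wave latent model with all unstandardised loadings fixed at one and item intercepts held equal over time. Residuals are linked across waves: "We included a priori correlated residuals for each item with itself from pre- to post-intervention". The mNA-SI model is the same, applied to prompts with no stressor reported.

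For mNA-SI the loadings count as salient "for six of the seven items at both pre (average loading = .38; range = .22 to .58"); at post the mean is .45 and the range .26 to .77. Then: "The factor score determinacy coefficients equaled .82 at pre and .86 at post". Footnote 1 limits these coefficients: "All factor score determinacy coefficients reported are for participants with complete data" on the indicators.

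The scores are saved ("We then saved factor score estimates for each participant for their latent mNA-SI at pre and at post") and used in three ways:

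- **T1 comparison.** "Testing for group differences on the latent mNA-SI factor score estimates at pre-intervention revealed" no significant difference (t = -.06, df = 100, d = -.01).
- **Effect test.** Post score regressed on pre score and condition.
- **Stability.** The stressor-reactive section gives a pre-post r of .96 for mNA-SI, treats it as near-perfect stability, and contrasts it with .73 for mNA-SR.

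The SAP does not say how scores were computed, whether .96 is a correlation of saved scores or the model's latent correlation, whether condition was in the model, or in which metric the effect will be expressed.

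**The concern.** Regression-type factor scores from a joint two-wave model use all 14 indicators for both scores, so the pre score borrows from post answers. If the intervention moves the post items, it also moves the pre score, and adjusting for that score removes part of the effect being estimated. Bartlett scores, or a pre score built from pre items only, do not shift the baseline in this way.

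At stake are the size of the mNA-SI coefficient, the meaning of its T1 comparison, and the stability contrast with mNA-SR. The SAP's own figures give some evidence on which kind of score was saved.

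**Working it through.** **Inputs.** From the SAP: the mNA-SI loadings, determinacies .82 and .86, r = .96, and df = 100 (so n = 102). Assumed, because not reported: individual loadings, latent correlation, same-item residual correlations and latent variance ratio. Also assumed at first: no condition term, no residual correlations within a wave, complete data.

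**1. Can pre items alone give .82?** With unit loadings, own-wave determinacy is D = sqrt(a/(1+a)), where a is the sum of l²/(1-l²).

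- Typical profile .22, .30, .35, .38, .40, .43, .58 (mean .38): a = 1.382, D = .76.
- Most favourable profile after rounding, six items salient: .215, .295 three times, .425, .585 twice (mean .385). a = .048 + .286 + .220 + 1.041 = 1.595; D = sqrt(1.595/2.595) = .784.
- Without the six-of-seven rule: .215 three times, .295, .585 three times. a = 1.802, D = .802.

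So .82 is out of reach from pre items under these assumptions. The post figure does not discriminate: own-wave D is .85-.88 and .86 is reported. Negative within-wave residual correlations can lift the pre limit above .82, so this step alone is not proof.

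**2. Do joint regression scores reproduce all three figures?** Scores are Φ Λ' Σ⁻¹ applied to the 14 items. Illustration: pre loadings .22, .30, .32, .34, .39, .51, .58; post loadings .26, .32, .36, .40, .47, .57, .77; equal latent variances; latent r .895; same-item residual correlations .50.

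| Quantity | Joint regression | Bartlett | Own-wave regression | SAP |
|---|---|---|---|---|
| Determinacy, pre / post | .821 / .860 | – | .767 / .856 | .82 / .86 |
| Pre-post score r | .959 | .752 | .751 | .96 |

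A wide search varied the loading profiles, with residual correlations 0-.9 by item and latent variance ratio .7-1.4 (280,000 settings, each figure matched within .005):

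- 2,688 settings matched with joint regression scores, none with Bartlett and none with own-wave scores.
- Where joint determinacies matched .82/.86 (6,873 settings), Bartlett r was at most .944 and own-wave r at most .900.
- With within-wave residual correlations allowed, own-wave settings matching both determinacies reached r of at most .93. Bartlett matched only when near-singular residual matrices were admitted (3 of 248,467 settings) or the tolerance was widened to .02 (23 of 175,033).

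These counts show what is attainable; they are not probabilities about the trial.

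**3. Consequence if joint scores were used.** For a true latent post shift Δ, in the illustration the post score moves .671Δ, the pre score moves .373Δ, and the slope is 1.005.

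- Joint: .671 - 1.005 × .373 = .296, so about 30% is recovered.
- Own-wave regression: the pre score does not move and the post score moves by D² = .856² = .733, so 73%.
- Bartlett: 100%.

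A true .50 SD effect is thus estimated as .15, .37 or .50 latent SD. Over matched settings, joint recovery runs from about 25% to just under 50%. It falls to 21% at the low end if some participants have pre items only or within-wave residual correlations are allowed.

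**4. T1 comparison.** A .50 SD post effect moves the pre score by .50 × .373 = .187. Divided by the pre-score SD of .821, that appears as a baseline d of .23 (.20-.28 over matched settings). The reported d is -.01, with approximate 95% limits -.01 ± 1.96 × sqrt(4/102), or -.40 to .38 (equal groups assumed).

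**5. Stability.** Latent r in matched settings is .87-.94, so .96 would be .02-.09 too high.

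**6. The test itself.** Without any intervention effect nothing leaks into the pre score, so type I error holds. In matched settings the test statistic loses about 3-8%. A .50 SD effect in residual-SD units is .62 (joint), .65 (own-wave) or .66 (Bartlett).

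**The case against.** The strongest objection is that the inference needs .96 to be a correlation of saved scores, and the SAP does not say so. If .96 is the model's latent correlation, .82 and .86 are still just attainable: the lowest pre determinacy found was .822, in settings with average same-item residual correlations of about .78-.88. The figures would then say nothing about which scores were saved, and Bartlett scores would remain possible. This stands as a condition on the claim. It is the less natural reading: the .73 for mNA-SR in the same sentence must come from saved residuals, and such settings were rare (66 of 84,489 that matched the post determinacy).

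Nor does the determinacy settle the matter alone. It shows which model produced the coefficient, not which scores were saved. That also stands, and it is why the argument rests on the three figures together.

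A third objection is that little is lost: the p-value is almost unaffected, the SAP promises no raw or latent-SD effect size, and mNA-SI does not appear in the protocol. This is right and limits the severity.

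A reader might also infer that the average mNA and stressor-present scores are contaminated. The documents do not show it. For average mNA, "The factor score determinacy coefficients equaled .89 at both pre and post", within the own-wave ranges of .89-.92 and .87-.91. For the stressor-present model, "The factor score determinacy coefficients equaled .87 at pre and .86 at post", within .86-.89 and .85-.88.

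**Conclusion.** The concern holds conditionally, for mNA-SI only. If .96 is a saved-score correlation and condition was not in the model, the SAP's figures fit joint two-wave regression scores and, under ordinary settings, neither Bartlett nor own-wave scores. The pre covariate then contains post-intervention information. The raw or latent-SD coefficient recovers about 25-50% of a true shift, of which the drop from 100% to about 73% is ordinary regression-score shrinkage. The T1 comparison is not of baseline alone, and .96 overstates a latent stability of about .87-.94, so setting it against .73 for mNA-SR does not compare like with like.

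Three stronger readings are not supported:

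- **Post answers were certainly used at baseline.** This is an inference from reported figures.
- **The mNA-SI or primary mNA test is invalid.** Type I error is intact, the mNA-SI statistic changes by a few percent, its residual-SD effect barely changes, and no harm to the primary mNA test is shown.
- **The reported T1 d of -.01 reveals or excludes a leak.** Its interval is too wide for either.

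mNA-SR uses the mNA-SI score, but the documents do not allow the size or direction of any effect there to be established. Severity is minor to should-fix, for a secondary measure.

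**What to change.** Estimate the mNA-SI condition effect in one step inside the latent model, regressing latent post on latent pre and condition. Protocol section 8.0 already describes an SEM test for the primary mNA path, so the approach is familiar to the team; this does not make the mNA-SI analysis a departure from the protocol.

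If saved scores are kept, use Bartlett scores or score pre from pre items only, and redo the T1 comparison on those scores.

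In either case, name the scoring method and the effect-size metric, say whether .96 is a latent or saved-score correlation, and base the stability statement on the latent correlation.

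The cost is SAP wording and a re-run of existing models, with no new data. Under the stated model the one-step SEM loses no power: with the condition-pre covariance free, it tests the same contrast as the joint-score regression. Fixing that covariance at zero, as randomisation permits, or using Bartlett scores raises the mNA-SI test statistic by about 3-9%. Wave-separate scores usually gain slightly but lose up to 10% in a few settings.
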